11.6 Frequency of review of cumulative data

All the data from the first part of the study (including the results of the blood nicotine analyses) will be reviewed by the leadership group, including [name], before initiation of the next part. If necessary, the doses planned for the next part or the timing of the blood samples may be adjusted accordingly and a modification of study protocol submitted to the IRB.

11.7 Statistical tests

Statistical methods will be used to analyze the safety data to determine whether harms are occurring. Paired sample t-test (or nonparametric Wilcoxon Rank-Sum test) will be used to examine the changes in the outcome measures (plasma nicotine, subjective measures, HR, BP) from the baseline.

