Participants will receive one film at this visit after completing baseline measures (approximately 8 AM). They will be instructed to allow the film to dissolve in their mouth without chewing or swallowing it and to report to the researcher when he or she feels that the film has completely dissolved. Four participants each will receive a randomly allocated dose of either (a) 0mg, (b) 2mg or (c) 4mg oral nicotine film. The Time and Events table above details the order of events and timing for biomeasures, questionnaires and 11 total blood draws. However, if the film dissolves within one minute of a set blood draw time, the blood draw that is to be completed one minute after the film dissolves will be omitted.

Payment:

Participants will receive \$120 for completing this visit.

Part 2- Screening (Phone)

Participants will be instructed to drink water prior to their visit to help the blood draw process go smoothly. They will also be instructed that they may choose to have meals from our cafeteria but may also bring snacks if they would like. Participants will also be informed that they can bring personal items such as laptops, books, etc. for use during their visit.

Part 2- Screening (In Person)

Participants will be re-screened for eligibility and informed consent for the appropriate part of the study will be obtained by research staff.

After consent, additional eligibility screening materials will include:

1. A review of medications and medical history
2. NIDA Drug Screener
3. Blood Pressure (systolic must be \leq 140 mm Hg, diastolic must be \leq 90 mm Hg)
4. Urine pregnancy test (if applicable)
5. Exhaled Carbon Monoxide <12 ppm

Part 2 Visit- 12 hours

Clinical measures and questionnaires will be conducted as outlined in the table below.

An IV will be inserted for access for 20 blood draws in Part 2. Time and contents of participant meals/snacks will also be recorded so as to enable researchers to assess food intake and timing as it relates to timing of nicotine absorption from the film.

Part 2: Time and Events Table														
	Screening		Part 2 Procedures											
Study Hour	-2	-1	0	1	2	3	4	5	6	7	8	9	10	11
Administer Film			X			X			X			X		
Blood Draws														
Baseline Blood		X												
Hour 0 Blood			Min 30, 45											
Hour 1 Blood				Min 0										
Hour 2 Blood					Min 0									
Hour 3 Blood						Set Mins: 0, 30, 45								
Hour 4 Blood							Min 0							
Hour 5 Blood								Min 0						

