Hour 6 Blood									Set Mins: 0,30,45					
Hour 7 Blood										Min 0				
Hour 8 Blood											Min 0			
Hour 9 Blood												Set Mins: 0, 30,45		
Hour 10 Blood													Min 0	
Hour 11 Blood														Min 0
Study Hour	-2	-1	0	1	2	3	4	5	6	7	8	9	10	11
Measures														
Screener 2	X													
Concomitant Medications	X													
Medical History	X													
NIDA	X													
CES-D	X													
Oropharyngeal Exam		X												X
Blood Pressure & Heart Rate	X	X	Min 30	Min 0, 30	Min 0, 30	Min 0, 30	Min 0, 30	Min 0, 30	Min 0, 30	Min 0, 30	Min 0, 30	Min 0, 30	Min 0, 30	Min 0
CO Reading	X													
Pregnancy Test	X													
Anthropometrics	X													
Demographics	X													
Dependence	X													
Cigarette Details	X													
Tobacco Use History		X												
Minnesota Withdrawal Scale		X	Min 50	Min 50		Min 50	Min 50		Min 50	Min 50		Min 50		Min 50

Questionnaire of Smoking Urges		X	Min 50	Min 50		Min 50	Min 50		Min 50	Min 50		Min 50	Min 50
Study Product Side Effects			Min 50	Min 50		Min 50	Min 50		Min 50	Min 50		Min 50	Min 50
Study Product Evaluation						Min 0							X
Likelihood of Use Scale						Min 0							X
Dose Awareness													X
Payment													\$240

Film Administration, Dosing and Blood draws:

Participants will receive four doses of nicotine film during this visit. Four participants each will be randomly allocated to consume four films over twelve hours in the following orders (a) 0,0,0,0mg (b) 2,2,2,2, or (c) 4,4,0,4. The first film will be administered upon completion of baseline measures (approximately 8AM). Again, participants will be instructed to allow the film to dissolve in their mouth, without chewing or swallowing it and to report to the researcher when he or she feels that the film has completely dissolved. Films will be administered every three hours (approximately 11 AM, 2 PM, and 5 PM). The Time and Events table above details the order of events and timing for biomeasures, questionnaires and 20 total blood draws.

Payment:

Participants will receive \$240 for completing this visit.

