7.4.2 Treatment Regimen

Nicotine films will be administered orally. They are used by placing a film on the tongue, closing the mouth and pressing the tongue gently to the roof of the mouth. The film will dissolve in the mouth within 5-10 minutes. Three doses of nicotine film will be used in this study: 0, 2, and 4 mg. During the first part, participants will receive one dose of either 0, 2, or 4 mg film. After the first part is complete, reactions to dosing will be evaluated and adjustments will be made if necessary before proceeding to the second part. Should adjustments need to be made, modified protocol and consent documents will be submitted to the IRB prior to proceeding to Part 2. During the second part, participants will receive four doses of nicotine film at three hour intervals over the course of twelve hours. There will be three dosing groups and four participants each will receive all 0 mg films, all 2 mg films, or a sequence of 4,4,0,4 mg films.

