9.0 Statistical Plan

9.1 Sample size determination

Initial testing by [name] (a principal investigator on the project and co-inventor of the oral nicotine film) has demonstrated that the plasma nicotine levels produced by oral nicotine film are comparable in size to those produced by consumption of a similar dose of Nicorette gum. Pharmacokinetic studies have shown that Nicorette gum has robust effects on plasma nicotine concentration that are readily detectable in sample sizes that are approximately the same as (e.g., Benowitz, Jacob, & Savanapridi, 1987; Lunell & Lunell, 2005), or smaller than (e.g., Shiffman et al., 2009), the one proposed here (n=12). Based upon such work, we are confident that we will have sufficient power to achieve the aim of the proposed research.

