11.2 Data that are reviewed

Data that will be reviewed include:

- Accrual and retention
- Adverse events and serious adverse events
- Protocol deviations/violations
- Changes in subjective effects (particularly dizziness and nausea, the most common nicotine effects)
- Changes in heart rate and blood pressure
- Oropharyngeal changes

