16.0 Number of Subjects

Participants will be screened until twelve participants have completed each part of the study protocol. Participants may elect to participate in one or both parts. We anticipate that fifty participants will be enrolled in order to account for screen failures after the consent form is signed.

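### With four participants per dose and no comparison with 0 mg, the paired tests in section 11.7 say little about harm in either direction and should give way to by-dose description

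*Combined protocol and SAP*

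**What the plan says.** Section 11.7 gives the tests a purpose: "Statistical methods will be used to analyze the safety data to determine whether harms are occurring". It then names the method: "Paired sample t-test (or nonparametric Wilcoxon Rank-Sum test) will be used to examine the changes in the outcome measures". The outcomes listed are plasma nicotine, subjective measures, heart rate and blood pressure, and the sentence repeats section 9.2.

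The groups are small in both parts. For Part 1, section 7.2 says "Four participants each will receive a randomly allocated dose of either (a) 0mg, (b) 2mg or (c) 4mg oral nicotine film". For Part 2 it says "Four participants each will be randomly allocated to consume four films over twelve hours", and section 7.4.2 agrees. Section 16.0 fixes the total: "Participants will be screened until twelve participants have completed each part of the study protocol".

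Sections 9.1, 9.2 and 11.7 give no significance level, sidedness, effect size, SD or harm threshold. They do not say whether the tests are run by dose or pooled, include no contrast with the 0 mg group, and have no rule for the repeated time points. Section 11.2 lists items for review, among them "Changes in heart rate and blood pressure", adverse events and oropharyngeal changes. Adverse events and oropharyngeal changes are not among the outcomes tested in 11.7.

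**The concern.** Section 11.7 is the only place where the safety plan names a statistical method for judging harm. The method looks unsuited to that task for three reasons.

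- Four people per dose give very little power.
- The non-parametric test named does not fit paired data. Its paired counterpart cannot reach the usual level with four people.
- A change from baseline within a group is uncontrolled. Section 12.0 expects nicotine withdrawal symptoms, possibly worse on placebo. Part 2 runs for twelve hours with meals, whose timing section 7.2 records because it may bear on nicotine absorption. A shift in heart rate, blood pressure or symptoms could therefore come from withdrawal, time or food. The randomised 0 mg group exists to separate these, and the test ignores it.

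Section 11.6 has all Part 1 data reviewed before repeated dosing starts, with no statistical criterion stated. A table of non-significant tests could carry more weight in that review than it deserves, and a chance significant result could be taken for a drug effect.

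**Working it through.** **Inputs from the document.** Four participants per dose group and 12 per part (7.2, 7.4.2, 16.0). Post-film heart-rate and blood-pressure times from the tables in 7.2: Part 1 has 1 + 2 + 2 + 2 = 7; Part 2 has 1 + (10 × 2) + 1 = 22.

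**Assumptions, because the plan gives none.** Level 0.05, two-sided (one-sided also shown); 80% power as the benchmark; true mean changes of 0.5 to 2 SD; SD of heart-rate or blood-pressure change of 5 to 10 units; approximately normal changes for the t-test.

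**The plan's own figure.** 3 groups × 4 = 12 agrees with section 16.0. The statement in 9.1 that "we are confident that we will have sufficient power to achieve the aim of the proposed research" cannot be reproduced, because no level, power, effect or SD is given. It also argues from plasma nicotine, not from safety measures.

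**Paired t-test by dose, n = 4.** Power is the probability that a noncentral t with 3 degrees of freedom and noncentrality d√4 = 2d falls beyond ±3.182.

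| True mean change | Power |
|---|---|
| 0.5 SD | 11% |
| 0.8 SD | 21% |
| 1.0 SD | 29% |
| 1.5 SD | 53% |
| 2.0 SD | 76% |

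- 80% power needs 2.13 SD two-sided, or 1.65 SD one-sided.
- The 95% CI half-width is 3.182/√4 = 1.59 SD.
- With an SD of change of 5, 8 or 10 units, the change detectable with 80% power is 10.6, 17.0 or 21.3 units.
- For scale, 80% power at 1 SD would need 10 people per dose.

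**Rank tests.** With four pairs, the smallest exact two-sided signed-rank p is 2/2^4 = 0.125 (one-sided 0.0625). Rank-sum for 4 v 4 can reach 2/C(8,4) = 2/70 = 0.029, but it treats baseline and post-film values as independent groups, which they are not.

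**If arms are pooled.** With 12, the detectable change is 0.89 SD; with the 8 active participants, 1.16 SD. Both assume that everyone pooled shifts alike. If only the four 4 mg participants respond, simulated power of the test on all 12 is about 14% at 1 SD and 26% at 2 SD. Pooling does remove the p-value floor (2/2^12 = 0.0005), but not the mixing of placebo with active.

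**False positives.** Seven times × three measures (heart rate, systolic, diastolic) = 21 tests per dose in Part 1. If independent, the chance of at least one false positive is 1 − 0.95^21 = 66%. The measures are correlated, so this is an upper-end illustration.

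**Events.** The exact two-sided 95% upper limit for 0 of n is 1 − 0.025^(1/n): 60% for 0/4 and 37% for 0/8 active. The chance of seeing at least one case of a harm with a true rate of 10% in four people is 1 − 0.9^4 = 34%.

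**Difference from 0 mg, 4 v 4.** The 95% half-width is 2.447 × √(1/4 + 1/4) = 1.73 SD, assuming equal variances.

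**The case against.** The strongest reply is that harm detection in this protocol does not depend on these tests. Section 11.2 lists adverse events, symptoms, vital signs and oropharyngeal changes for review. Section 11.5 provides weekly review of adverse event forms and immediate review of serious cases, with a recommendation on continuing. Section 11.6 puts leadership review of all Part 1 data before Part 2. Section 3.3.1 has individual removal criteria. One person's severe reaction, which a mean change would hide, would be picked up there. All of this stands.

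A reader might therefore go too far in two ways. The first is to infer that the plan treats a non-significant test as evidence of safety, or uses it to release Part 2. No section says so: 11.7 attaches no threshold or action to a p-value. Misreading is a risk, not a planned step. The second is to infer that the tests can never show harm. That is literally true only of the signed-rank test run by dose at an assumed 0.05 level. The t-test, which is named first, can detect shifts of about 2 SD, and the plan does not say that the tests are run by dose.

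It can also be said that the test sentence comes from 9.2, so the misnamed rank test and the unstated grouping belong there as well. That is fair. What is particular to 11.7 is the purpose assigned to the tests and the lack of a controlled safety summary.

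**Conclusion.** The point holds in a limited form. The method named in 11.7 cannot reliably do the job that section gives it. By dose, it has 29% power for a 1 SD change and needs about 2.1 SD for 80%; the valid paired rank test stops at p = 0.125. Pooling helps only if all pooled participants shift alike, which a group including 0 mg makes implausible for a drug effect. Without the 0 mg contrast, a significant result need not be drug harm, and a non-significant one says almost nothing about its absence.

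The group sizes, the p-value floors and the event limits do not depend on an assumed SD. The power figures rest on a two-sided 0.05 level and normal changes. The size in heart-rate or blood-pressure units rests on assumed SDs of 5 to 10. The consequence for decisions is only a possibility, since case and leadership review run alongside. This should be corrected, but it is not a ground for holding up the study.

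**What to change.** In section 11.7:

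- Delete the clause that gives the tests the task of establishing harm, and remove the tests of safety measures.
- For each part, tabulate by dose the number of participants with each event the protocol already names: resting heart rate persistently above 100, nausea, vomiting, dizziness (3.3.1), systolic pressure above 160 (11.5) and oropharyngeal change (11.2). Give exact two-sided 95% CIs and state the upper limit when the count is zero (60% for 0/4, 37% for 0/8 active). Keep the parts separate, because 7.1 lets one person join both.
- List individual values and events by participant.
- Give each participant's maximum post-film change in heart rate and blood pressure by dose, with the difference from 0 mg and its 95% CI. The maximum of 7 or 22 readings tends upward even without a drug effect, so it should be read only against 0 mg.
- State that safety decisions rest on the case and leadership review in 11.5 and 11.6, not on a p-value.

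The cost is revised wording and a few tables from data already scheduled for collection. The intervals will be wide, about ±1.7 SD for 4 v 4. The change shows the uncertainty honestly and adds a control, but it does not increase the ability to detect harm.

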11.8 Suspension of research

Due to the low risk of the intervention, it is unlikely that there will be a need to suspend the research. However, should the study doctor ([name]) identify any issues after reviewing the data, they can develop stopping rules for the trial and these recommendations will be followed.

12.0 Risks

Potential risks for subjects are minimal. The nicotine films which will be administered to subjects have been previously tested in humans and we do not expect them to provide higher nicotine levels than subjects routinely receive from their smoking. Subjects will have a review of their medical history prior to entry into the study. Subjects will be under supervision throughout their participation in the study and adverse symptoms will be recorded and monitored by the Project Leaders. The major risks associated with the study are related to the use of nicotine (which is similar to the nicotine received from smoking) and nicotine withdrawal.

Additional potential risks include:

- **Nicotine withdrawal symptoms:** It is possible for subjects to experience short-term nicotine withdrawal symptoms (e.g. irritability, restlessness, difficulty concentrating, anxiety). Those receiving placebo films may experience more serious nicotine withdrawal symptoms.
- **Risk to fetus and breast fed infants:** Nicotine is known to be harmful to the developing human fetus, either from cigarettes or at the dose being used in this study. For this reason women must not be pregnant or nursing in order to participate in the study.
- **Risks of IV catheter for blood draw:** The discomfort associated with the IV insertion by venipuncture (by needle then catheter into a vein) for removing blood is a slight pinch or pin prick when the sterile needle enters the skin. The risks include mild discomfort and/or a black and blue mark at the site of puncture. Less common risks include a small blood clot, infection or bleeding at the puncture site, and on rare occasions fainting during the procedure.
- **Loss of confidentiality:** There is a risk of loss of confidentiality if information is obtained by someone other than the investigators. Precautions will be taken to prevent this including direct coding of data in REDCap.
- **Randomization:** Participants will be assigned to a treatment program by chance.
- **Discomfort from questionnaires:** It is possible that some of the questions in the questionnaires may make participants uncomfortable. They will be instructed that they are free to skip any questions that make them uncomfortable.
- **Nicotine film side effects:** Excess nicotine can cause mild symptoms such as nausea, dizziness, diarrhea and rapid heartbeat. Occasionally these symptoms are more severe (e.g. vomiting) such as when an individual receives more nicotine than they are accustomed to. This, however, is unlikely to occur with the doses used in this study. Additional side effects of the film may include hiccups.

- **Possible effects on the oral cavity.** In order to assess local toxicity of the study product, the CRC nurse assisting with the clinic visit will perform an oropharyngeal exam at the beginning of the visit prior to the participant receiving the study product as well as at the end of the visit after study product use is complete. Any changes will be assessed and documented. During the visit, after each film administration, participants will be asked to report side effects including any mouth discomfort or irritation via a questionnaire. If indicated, participant would discontinue study product use. Lesions of the oral mucosa are not anticipated as daily dissolution of several 2 mg sublingual nicotine tables (range 1-12/day over a 6 month period) led to only mild and transient effects on the oral mucosa[24]
- **Incidental Finding:** None of the tests carried out in this study are intended to provide diagnoses for clinical purposes, but participants will be alerted to findings that should be discussed with a healthcare provider (such as high blood pressure)

The participant may be removed from the research study without his or her permission because the participant does not follow the instructions for the study, has an adverse reaction to the study product (irregular heartbeat, palpitations, tachycardia (resting heart rate persistently greater than 100 beats per minute), has symptoms of nicotine overdose such as nausea, vomiting, dizziness, weakness, or rapid heartbeat, or has symptoms of an allergic reaction.

Participants are instructed to please call the Principal Investigator, [name] [name]., at [contact] during business hours or [contact] after business hours if they:

- Experience any symptoms after the study is completed that they believe may be related to participation in the study
- Have questions, complaints, or concerns about the research

13.0 Potential Benefits to Subjects and Others

13.1 Potential Benefits to Subjects

There are no guarantees of benefit for participation in this research.

13.2 Potential Benefits to Others

The main benefit to society and others from the study is the possibility of a greater scientific understanding of the safety and efficacy of nicotine film.

14.0 Sharing Results with Subjects

This study is not designed to diagnose any disease or condition. However, if during the course of conducting clinical procedures (e.g., blood pressure) a participant is found to have a result outside of clinical norms, the result will be discussed with the participant at the visit where the result is identified. The participant will be given a letter indicating what procedure was done and will direct them to contact a medical provider for further evaluation.

15.0 Economic Burden to Subjects

15.1 Costs

There are no costs that subjects will be responsible for related to the research.

15.2 Compensation for research-related injury

It is the policy of the institution to provide neither financial compensation nor free medical treatment for research-related injury. In the event of injury resulting from this research, medical treatment is available but will be provided at the usual charge. Costs for the treatment of research-related injuries will be charged to subjects or their insurance carriers.

16.0 Number of Subjects

Participants will be screened until twelve participants have completed each part of the study protocol. Participants may elect to participate in one or both parts. We anticipate that fifty participants will be enrolled in order to account for screen failures after the consent form is signed.

17.0 Resources Available

17.1 Facilities and locations

All participant visits will take place in the Penn State Hershey CRC.

17.2 Feasibility of recruiting the required number of subjects

The smoking prevalence in South Central Pennsylvania is 19% of the adult population. Our recruitment strategy is designed to broadly disseminate information about the study to members of the community

17.4 Availability of medical or psychological resources

Any urgent health problem will require accompanying the participant to the emergency room, which is located in the same building.

